4.10.4 Primary Endpoint

The primary endpoints for evaluation of pharmacokinetic comparability will be assessed using a linear fixed effects analysis of variance model with the natural logarithm of primary PK parameters (eg, AUCinf [for final analysis only], AUClast, Cmax and AUC0-91d [for IA only]) for the individual mAbs AZD8895 and AZD1061, as well as for the sum of the individual mAbs of AZD7442 (AZD8895 + AZD1061) as the response variables, treatment, injection site, anti-COVID-19 vaccination status (as reported on the CRF), and continuous baseline body weight on the log scale as fixed effects and participant as a random effect.

Transformed back from the logarithmic scale, geometric least square means (GLSM) together with CIs (2-sided 95%) will be estimated and presented by treatment. Also, ratios of geometric least square means together with CIs (2-sided 90%) will be estimated and presented.

The following treatment comparisons will apply:

- Treatment A vs Treatment B
- Treatment A vs Treatment C
- Treatment B vs Treatment C

where:

- Treatment A: 300 mg (total protein) AZD7442 as a single IM dose (co-formulation of 150 mg AZD8895 + 150 mg AZD1061) (clonal cell line material).

- Treatment B: 300 mg (total protein) AZD7442 as two separate IM doses of the individual mAbs (150 mg AZD8895 and then 150 mg AZD1061) (clonal cell line material).
- Treatment C: 300 mg (total protein) AZD7442 as two separate IM doses of the individual mAbs (150 mg AZD8895 and then 150 mg AZD1061) (cell pool material).

One statistical model will be fitted for each PK parameter, including all study data. Estimating parameters for the comparisons listed above will be done from this one model making use of the appropriate contrasts.

A variance component covariance structure will be used for the within-participant errors. Degrees of freedom will be determined using Kenward-Roger approximation.

If the estimating algorithms do not converge, these covariance structures will be tried: first-order autoregressive, compound symmetry, unstructured and Toeplitz.

Missing values will not be imputed. In this analysis it is thus assumed that any missing values are missing at random (MAR).

The following figures, in black and white, will be generated:

Figure	Analysis set	Presented by
Individual profiles, serum concentration versus actual elapsed time data – linear and semi-log scale, separate plot for each participant for the individual mAbs AZD8895 and AZD1061, as well as for the sum of the individual mAbs of AZD7442 (AZD8895 + AZD1061)	SAF	n/a
Combined individual serum concentration versus actual elapsed time data – linear and semi-log scale for the individual mAbs AZD8895 and AZD1061, as well as for the sum of the individual mAbs of AZD7442 (AZD8895 + AZD1061)	PK	
 • treatment
GMean (+/-gSD), serum concentration versus planned nominal time data – linear and semi-log scale for the individual mAbs AZD8895 and AZD1061, as well as for the sum of the individual mAbs	PK	
 • treatment • treatment and injection site • treatment and bodyweight category

of AZD7442 (AZD8895 + AZD1061)		
 • treatment, injection site, and bodyweight category
Individual PK parameter with geometric mean (95% CI) for Cmax, AUClast, AUCinf (for the final analysis only), and AUC0-91d (for the IA only) for the individual mAbs AZD8895 and AZD1061, as well as for the sum of the individual mAbs of AZD7442 (AZD8895 + AZD1061)	PK	
 • treatment • treatment and injection site • treatment and bodyweight category • treatment, injection site, and bodyweight category
Geometric least square means with 95% CIs for all treatments	PK	
 • primary PK parameters
Geometric least square means ratios with 90% CIs for all comparisons	PK	
 • primary PK parameters

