- Section **6.3.7:** Text regarding SARS-CoV-2 testing updated.
- Section **6.5.1:** Renamed to **CCI** [REDACTED] and moved text from section 6.6: **CCI** [REDACTED] Samples under this section.
- Section **6.6:** Renamed to Immunogenicity Assessments and moved text from section 6.5.1: Collection of Pharmacodynamic Samples (regarding analysis of blood samples for determination of serum anti-AZD8895 and anti-AZD1061) under this section.
- Section **11.2.4.1:** Added requirement for last dose of anti-COVID-19 vaccine received prior to randomization, to be recorded in the EDC system.
- Section **12.1:** Replaced Principal Investigator with Medical Monitor and provided contact details for the Medical Monitor.
- Reference list updated.
- Additional minor formatting and grammatical corrections were made.
- Minor inconsistencies in the original protocol were clarified throughout the protocol.

PROTOCOL SYNOPSIS

Title of the Study

Phase I, Randomized, Open label, Three-arm, Single Dose, Parallel Group Study to Compare AZD7442 (AZD8895 + AZD1061) Pharmacokinetic Exposure Following Intramuscular Administration as a Co-formulation versus Administration from Two Separate Vials of the Individual Monoclonal Antibodies in Adult Healthy Participants

Study Center

This study will be conducted at a minimum of three different Clinical Units.

Study Rationale

The study will assess pharmacokinetic (PK) comparability between different formulations of AZD7442, which is a combination of two individual monoclonal antibodies (mAbs), AZD8895 and AZD1061. The materials to be assessed will be:

- A co-formulation of clonal cell line material of AZD8895 + AZD1061 mAbs as a single intramuscular (IM) injection from a single mixture,
- Individual formulations of clonal cell line material of AZD8895 and AZD1061 mAbs as separate sequential IM injections, and
- Individual formulations of cell pool material of AZD8895 and AZD1061 mAbs as separate sequential IM injections.

An open label, parallel group design has been chosen for this single dose PK comparability study.

Number of Participants Planned

Approximately 207 evaluable participants will be enrolled in this study.

Study Period

Estimated date of first participant enrolled: November 2021 (signing of informed consent)

Estimated date of last participant completed: Q3 2023

Study Objectives

The objectives of the study are:

Primary Objectives:

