3. STUDY DESIGN

3.1. Overall Study Design and Flow Chart

This study will be an open label, randomized, three-arm, parallel group, single dose, study in healthy participants (males and females), performed at multiple study centers.

A total of 207 evaluable healthy male and female participants will be randomized in a 1:1:1 ratio between the three treatment groups (69 participants per group). Each participant will receive AZD7442 as either a single IM dose (co-formulation; AZD8895 + AZD1061) from a single vial or as two separate IM doses of the individual mAbs (AZD8895 and then AZD1061) from two separate vials from either clonal cell line material or cell pool material as follows:

- **Treatment A:** 300 mg (total protein) AZD7442 as a single IM dose (co-formulation of 150 mg AZD8895 + 150 mg AZD1061) (clonal cell line material).
- **Treatment B:** 300 mg (total protein) AZD7442 as two separate IM doses of the individual mAbs (150 mg AZD8895 and then 150 mg AZD1061) (clonal cell line material).
- **Treatment C:** 300 mg (total protein) AZD7442 as two separate IM doses of the individual mAbs (150 mg AZD8895 and then 150 mg AZD1061) (cell pool material).

The product in Treatment Groups A and B is derived from material that originated from a clonal cell line, with a separate cell line, GMP cell bank, and manufacturing process for AZD8895 and AZD1061. The product in Treatment Group C is derived from material that originated from a non-clonal cell pool, with a separate pool of cells, GMP cell bank, and manufacturing process for AZD8895 and AZD1061. The clonal cell line is derived from a subpopulation of the respective cell pool, and there are no differences in antibody sequence between these cell banks. These materials have been demonstrated to be analytically comparable to each other. Refer to [Table 5-1](#) for details on the IMP.

Additionally, within each of the treatment groups, participants will be randomized 1:1:1 to one of the three injection sites:

- Lateral thigh,
- Gluteal dorsal,
- Gluteal ventral.

Further, participants will be stratified based on the body weight and vaccination status at randomization as follows:

[figure not shown]
- Body weight at randomization: < 70 kg; 70 to < 80 kg; and \geq 80 kg
- Anti-SARS-CoV-2 vaccination status at randomization: non-vaccinated or vaccinated (with one or more locally approved/authorized COVID-19 vaccine doses)

The study will comprise of:

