4. STUDY POPULATION

4.1. Selection of Study Population

The investigator should keep a participant screening log of all potential participants who consented and were subjected to screening procedures.

Participants who fail to meet the inclusion criteria or any exclusion criterion should not, under any circumstances, be randomized or dosed in the study. There can be no exceptions to this rule.

This study will be conducted in male and female participants. The study may not necessarily be balanced regarding gender. The study was not formally powered to detect differences between genders for the primary endpoint. It is not planned to perform sub-analyses on gender.

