5. STUDY CONDUCT

5.1. Participant Enrollment and Randomization

The investigator (or designee) will ensure:

- Signed informed consent is obtained from each potential participant before any study specific procedures are performed.
- Each potential participant is assigned a unique enrollment number at screening upon signing the Informed Consent.
- The eligibility of each participant is in accordance with the inclusion and exclusion criteria.
- Each eligible participant is assigned a unique randomization code.

Randomization will be done on Day 1 before IMP dosing. Randomization codes will be assigned strictly sequentially as participants become eligible for randomization (codes to be used without leading zeros). Randomization numbers will be generated within the AstraZeneca randomization system (AZRand).

The enrollment number will be used to identify the participant during the screening process and throughout study participation, if applicable, and will be recorded in the eCRF. This number will be composed of two parts: the first part will have 4 digits (fixed) representing the study Clinical Unit site identifier. The second part will have 3 digits (ascending) which will be assigned sequentially within each study Clinical Unit starting with 001.

If a participant withdraws his/her participation in the study, then his/her enrollment/randomization code cannot be reused. For each treatment sequence, an additional set of random numbers will be generated with AZRand.

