11.2.6.6. Statistical Analysis for Pharmacokinetic Comparability

Pharmacokinetic comparability will be assessed between Treatment A versus Treatment B, Treatment A versus Treatment C, and Treatment B versus Treatment C based on the PK analysis set.

Analyses will be performed using a linear fixed effects analysis of variance model using the natural logarithm of primary PK parameters (eg, AUCinf, AUClast, and Cmax) for the individual mAbs AZD8895 and AZD1061, as well as for the sum of the individual mAbs (AZD8895 + AZD1061) as the response variables, treatment, injection site, anti-COVID-19 vaccination status, and continuous baseline body weight on the log scale as fixed effects and participant as a random effect. Transformed back from the logarithmic scale, geometric means together with CIs (2-sided 95%) for AUCs and Cmax will be estimated and presented. Also, ratios of geometric means together with CIs (2-sided 90%) will be estimated and presented.

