4.14 Changes to Protocol-planned Analyses

During scheduled audits of the sites #7808 and #7809, irregularities and critical findings were observed regarding collection and handling of study data. A subsequent FDA inspection also had several critical findings for data quality at these sites. Hence a sensitivity analysis is deemed necessary to analyze the robustness of the primary analysis of the trial. The sensitivity analysis will be performed on the primary and secondary endpoints including safety data and ADA endpoints.

The sensitivity analysis will be performed on the primary PK endpoints evaluating the comparability between the three treatment arms. Secondary PK endpoints, safety and ADA endpoints will also be analyzed. Demographic summary tables (excluding site #7808 and #7809) will be produced to provide details for the sensitivity analysis.

The sensitivity analysis will repeat planned analyses of the above-mentioned endpoints by excluding the sites: #7808 and #7809 to provide evidence for the robustness of the primary analysis, which include all sites (including sites: #7808 and #7809). A complete list of repeated analyses will be included in the TFL shells.

Additional PK analysis of AUC_{inf}, AUCl_{ast} and C_{max} similar to that described in Section 4.10.4 will be performed for specified subgroups of lateral thigh group, gluteal dorsal group and gluteal ventral group for each compound AZD8895, AZD1061 and AZD7442.

Further subgroup analysis will be performed by injection site within treatment group, by vaccination status within treatment group, and by body weight category within treatment group for each compound AZD8895, AZD1061 and AZD7442.

The mixed model specifications will be described in the footnotes of each subgroup analysis table.

Forest plots of the additional comparisons will present the geometric mean ratio point estimate and corresponding 90% CI. These will include the injection site vaccination status, and body weight category subgroup comparisons grouped by treatment.

Approval Signatures

Document Name: Statistical Analysis Plan 27 Oct 2023 D8850C00009

Document Number: VV-TMF-4986002

Parexel Version Number:

System Version Number: 5 .0

Document Approvals		
Reason for signing: Approved	Name: PPD	Role: PPD
Reason for signing: Approved	Name: PPD	Role: PPD

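### The primary PK model omits Clinical Unit and sex, which are recorded for every participant: a possible modest loss of precision, not a bias

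*SAP*

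**What the plan says.** SAP 4.10.4 fits the log of each primary PK parameter with "treatment, injection site, anti-COVID-19 vaccination status (as reported on the CRF), and continuous baseline body weight on the log scale as fixed effects", plus participant as a random effect. Protocol 11.2.6.6 has the same terms: "treatment, injection site, anti-COVID-19 vaccination status, and continuous baseline body weight on the log scale as fixed effects and participant as a random effect". The two documents agree, and neither lists Clinical Unit or sex.

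On randomisation, Protocol 3.1 states that "participants will be stratified based on the body weight and vaccination status at randomization as follows", naming three weight categories and two vaccination groups. It adds that "within each of the treatment groups, participants will be randomized 1:1:1 to one of the three injection sites". Protocol 5.1 says that "Randomization codes will be assigned strictly sequentially as participants become eligible for randomization". No stratification or blocking by unit or by sex is stated.

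On the omitted factors, the protocol synopsis says "This study will be conducted at a minimum of three different Clinical Units". The unit identifier is the first four digits of every enrolment number (Protocol 5.1), and sex is among the demographic variables (Protocol 11.2.3.1). Protocol 4.1 notes that "The study may not necessarily be balanced regarding gender" and plans no sub-analysis by gender.

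SAP 4.14 reports that at sites 7808 and 7809 "irregularities and critical findings were observed regarding collection and handling of study data". It plans to repeat the analyses without those two sites. The subgroup analyses that it adds cover injection site, vaccination status and weight category, not unit or sex.

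**The concern.** Injection, sampling and first handling of the samples all take place in the Clinical Unit, so unit is a natural source of variation in measured exposure. Sex may be another, beyond what body weight explains. With neither in the model, any such variation stays in the residual and widens every primary interval. The participant random effect cannot absorb it: each model has one value per participant, so that term cannot be separated from the residual.

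What is at stake is interval width. Comparability requires the 90% intervals for AUC and Cmax to lie within 0.8000 to 1.2500 in all three comparisons (Protocol 11.1.1). The most variable parameter, AZD1061 Cmax, has the least room.

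**Working it through.** **Inputs from the documents.** 69 per group, true ratio 1, limits 0.8 to 1.25, two-sided 90% interval (two one-sided 5% tests), and a CV for AZD1061 Cmax of 38.5% (Protocol 11.4, SAP 4.12). The share of residual variance explained by unit and sex together, R², is not in the documents. It is assumed below.

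**The plan's own figure.**
- Log-scale SD = √ln(1 + 0.385²) = 0.372.
- SE of a difference between two arms = 0.372 × √(2/69) = 0.0633.
- Power of the two one-sided tests with limits ±ln 1.25 = ±0.223, integrating over the distribution of the residual variance (136 df): 93.8%. The normal approximation gives 94.0%.

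This is close to the stated 95% but strictly just below it; 73 per group would give 95.0%. On the same method AZD8895 Cmax has 96.7%, AZD1061 AUCinf 96.0%, and the other AUCs at least 99.4%. All figures are per parameter and per comparison.

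**Adding unit and sex.** The planned model uses 7 parameters (intercept, 2 treatment, 2 injection site, 1 vaccination, 1 weight), leaving 207 − 7 = 200 df. Sex takes 1 more and k units take k − 1, leaving 197 df for 3 units or 192 for 8. The SE is multiplied by √(1 − R²). For AZD1061 Cmax:

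| Assumed R² | SE multiplier | Fall in SE | Power | Upper 90% limit at ratio 1 |
|---|---|---|---|---|
| 0 | 1.000 | none | 93.8% | 1.110 |
| 5% | 0.975 | 2.5% | 95.0% | 1.107 |
| 10% | 0.949 | 5.1% | 96.0% | 1.104 |
| 15% | 0.922 | 7.8% | 97.0% | 1.101 |

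At R² = 0 the lost degrees of freedom change power by less than 0.1 point with either 3 or 8 units.

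**Baseline.** The table takes 0.372 as the residual SD after the planned covariates. The documents do not say whether the 38.5% is adjusted for anything. If weight, injection site and vaccination status already removed 10% of that variance, power would be about 96.0% before unit or sex entered. A further 5% would leave 0.90 × 0.95 = 0.855 of the variance, close to the 15% row (97.0%). The gain would then be about 1 point.

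**The case against.** The case for leaving the model alone is respectable. It adjusts for both stratification factors and for the randomised injection site, so it matches the design, and the protocol and SAP agree. Every effect size above is assumed. The power figures concern the most variable parameter only. The log-weight term and the weight strata already deal with the part of any sex difference that runs through weight. All of this stands, and it limits the point to precision.

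Three stronger readings are tempting, and the documents do not support them.

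- *The ratios are biased.* They are not. Allocation is randomised, so the intervals are valid without these terms. The sentence on gender balance most naturally describes overall enrolment, not a difference between arms.
- *Chance imbalance between arms is a second harm, on top of the wider interval.* It is the same sampling error, and the interval already covers it.
- *The findings at sites 7808 and 7809 show that measured exposure differs by unit.* SAP 4.14 reports problems in collecting and handling data. It does not report shifted concentrations, and the documents do not give those sites' share of participants.

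The planned exclusion analysis is also the better check on unreliable data. A unit term removes only an average shift and keeps the doubtful values. It does not, however, adjust for differences among the remaining units, so the two analyses answer different questions.

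Timing is a fair objection too. The SAP is dated 27 October 2023, after the estimated last completion in Q3 2023, in an open-label trial with the site findings already known. Changing the primary model at that stage would invite criticism as post hoc.

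**Conclusion.** The point holds as a modest matter of precision. Two factors recorded for everyone are left out of the primary model, and adding them costs almost nothing. If they explain 5% to 15% of residual log variance, which is an assumption, AZD1061 Cmax gains roughly 1 to 3 points of power per comparison. The gain is smaller if the planned covariates already reduce the variance, and nil if unit and sex explain nothing. Parameters with power already near 99% have little to gain. Clinical Unit is the stronger of the two terms, because log weight already covers much of any sex effect. Nothing here makes the planned primary analysis invalid.

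**What to change.** Specify one model per PK parameter that adds Clinical Unit and sex as fixed effects to the planned terms, and use it for all three contrasts (A versus B, A versus C, B versus C). State the rule for pooling small units in advance, without reference to results by arm.

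Make this the primary model only if it is fixed before database lock, in a new SAP version. If the database is locked, keep the planned primary model and report this one as a named supportive analysis through an SAP addendum, the route that SAP section 1 provides. In either case keep the analysis excluding sites 7808 and 7809; the new model sits beside it and does not replace it.

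The cost is SAP wording, a pooling rule, one further set of tables if the model is supportive, and 3 degrees of freedom with three units or 8 with eight, out of about 200.

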- Secondary PK parameters: Tmax, AUC0-31d, AUC0-61d, AUC0-91d, AUC0-181d, tlast, t½λz, CL/F, and Vz/F.

Additional PK parameters may be determined where appropriate.

Exploratory Endpoints:

- CCI

Statistical Methods

Analysis Sets

The safety analysis set will include all participants who were randomized and received any amount of IMP. The PK analysis set will consist of all participants in the safety analysis set who received IMP and have evaluable serum PK data, with no important protocol deviations thought to impact on the analysis of the PK data. The Randomized Set will consist of all participants randomized into the study.

Presentation and Analysis of Pharmacokinetic Data:

The serum concentrations and PK parameters will be listed and presented in tabular and graphical form, as appropriate for the individual mAbs AZD8895 and AZD1061, as well as for the sum of the individual mAbs of AZD7442 (AZD8895 + AZD1061). The serum concentrations for each scheduled time point will be summarized by treatment group, treatment group and injection site, treatment group and bodyweight category, and treatment group, injection site, and bodyweight category using appropriate descriptive statistics, based on the PK analysis set for the individual mAbs AZD8895 and AZD1061, as well as for the sum of the individual mAbs of AZD7442 (AZD8895 + AZD1061). The PK parameters will be derived using non-compartmental methods for the individual mAbs AZD8895 and AZD1061, as well as for the sum of the individual mAbs of AZD7442 (AZD8895 + AZD1061). All PK parameters will be summarized by treatment group, treatment group and injection site, treatment group and bodyweight category, and treatment group, injection site, and bodyweight category using appropriate descriptive statistics, based on the PK analysis set.

The natural log transformed primary PK parameters (eg, AUCinf, AUClast, and Cmax) will be analyzed using a mixed effects model with treatment, injection site, anti-COVID-19 vaccination status, and continuous baseline body weight on the log scale as fixed effects and participant as a random effect. Transformed back from the logarithmic scale, geometric means together with confidence intervals (CIs) (2-sided 95%) for AUCinf, AUClast, and Cmax, will be calculated and presented. Also, ratios of geometric means together with CIs (2 sided 90%) will be estimated and presented.

[figure not shown]

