3 INVESTIGATIONAL PLAN

3.1 Overall Study Design and Plan

This is an open label, randomized, three-arm, parallel group, single dose, study in healthy participants (males and females), performed at multiple study centers to assess pharmacokinetic (PK) comparability between different formulations of AZD7442, which is a combination of two individual monoclonal antibodies (mAbs), AZD8895 and AZD1061. Each participant will receive AZD7442 as either a single IM dose (co-formulation; AZD8895 + AZD1061) from a single vial or as two separate IM doses of the individual mAbs (AZD8895 and then AZD1061) from two separate vials from either clonal cell line material or cell pool material as follows:

- Treatment A: 300 mg (total protein) AZD7442 as a single IM dose (co-formulation of 150 mg AZD8895 + 150 mg AZD1061) (clonal cell line material).
- Treatment B: 300 mg (total protein) AZD7442 as two separate IM doses of the individual mAbs (150 mg AZD8895 and then 150 mg AZD1061) (clonal cell line material).
- Treatment C: 300 mg (total protein) AZD7442 as two separate IM doses of the individual mAbs (150 mg AZD8895 and then 150 mg AZD1061) (cell pool material).

Additionally, within each of the treatment groups, participants will be randomized 1:1:1 to one of the three injection sites:

- Lateral thigh,
- Gluteal dorsal,
- Gluteal ventral.

Further, participants will be stratified based on the body weight and vaccination status at randomization as follows:

[figure not shown]
- Body weight at randomization: < 70 kg; 70 to < 80 kg; and \geq 80 kg
- Anti-SARS-CoV-2 vaccination status at randomization: non-vaccinated or vaccinated (with one or more locally approved/authorized COVID-19 vaccine doses)

The study will comprise of:

- A Screening Period of up to 28 days that requires participants to visit the Clinical Unit (Visit 1).
- A Treatment Period of 1 day (Day 1; Visit 2) during which participants will be admitted to the study Clinical Unit and be randomized to receive their dose of IMP (AZD7442 as either a single IM dose or two separate IM doses). Participants will stay at the study clinic for at least 8 hours after dosing and will be discharged from the Clinical Unit at the discretion of the investigator, on the same day.
- A Follow-up Period of approximately 1 year consisting of regular visits to the study Clinical Unit starting from the day after dosing, Day 2 through to Day 361. The subsequent study visits total in 11 outpatient follow-up visits (Visits 3 to 13).

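### Does the redundant participant random effect in the primary PK model put the 90% confidence intervals in doubt?

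*SAP*

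**What the plan says.** The SAP (3.1) describes the trial in these terms: "This is an open label, randomized, three-arm, parallel group, single dose, study in healthy participants". Each participant is dosed once, with one of three treatments, and one AUCinf, one AUClast and one Cmax are derived for each analyte.

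SAP 4.10.4 calls the primary model a "linear fixed effects analysis of variance model" and in the same sentence ends its list of terms with "continuous baseline body weight on the log scale as fixed effects and participant as a random effect". It continues: "A variance component covariance structure will be used for the within-participant errors". Degrees of freedom are by Kenward-Roger. For fitting trouble it says: "If the estimating algorithms do not converge, these covariance structures will be tried: first-order autoregressive, compound symmetry, unstructured and Toeplitz".

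The protocol has the same mixture. Section 11.2.6.6 states "Analyses will be performed using a linear fixed effects analysis of variance model" and then includes participant as random. The synopsis says the log parameters "will be analyzed using a mixed effects model with treatment, injection site, anti-COVID-19 vaccination status" and the remaining covariates.

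The primary output is three geometric mean ratios (A/B, A/C, B/C) per parameter and analyte, each with a two-sided 90% CI to be held against 0.80 to 1.25.

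**The concern.** A participant random effect and a within-participant error structure need at least two values per participant. Here there is one, and the model has no period, time or analyte term that would create a repeated factor. Three difficulties seem to follow.

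- The two variances are completely confounded, so the information matrix for them is singular. Kenward-Roger uses its inverse, which does not exist.
- The four fallback structures all model correlation between repeated values, so none can cure non-convergence. Dropping the participant term, which would cure it, is not listed.
- The same model is called both fixed effects and mixed effects.

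The 90% CIs from this model are the trial's answer. If their degrees of freedom depended on how software treats a singular matrix, or if the final model had to be chosen after seeing data in an open-label trial, the comparability conclusion would rest on something not prespecified.

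**Working it through.** **Inputs.** 69 per group, 207 in total (protocol 3.1 and 11.4). Mean parameters: intercept 1 + treatment 2 + injection site 2 + vaccination status 1 + log weight 1 = 7. Planning CVs: protocol Table 11-1, the largest being 38.5% (AZD1061 Cmax). Margins: 0.80 and 1.25.

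**The plan's own figure.** The stated power is at least 95% at a true ratio of 1. With s = √ln(1 + CV²), a CV of 38.5% gives s = √0.1382 = 0.3718 and SE = 0.3718 × √(2/69) = 0.0633. Power of the two one-sided 5% tests, using the t distribution, is 93.8% with 136 df (two groups alone) and 93.8% with 200 df. AZD8895 Cmax gives 96.7%, AZD1061 AUCinf 96.0%, and the other AUCs 99.4% to 99.9%. The stated figure is reproduced to within about 1 point at worst. The small shortfall at 38.5% is a sample-size matter; the choice of df does not affect it.

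**Step 1: what is identifiable.** With one row per participant, V = (σ²_participant + σ²_residual) × I = σ² × I. The fixed-effect estimates do not depend on σ², and their variance is σ²(X′X)⁻¹. Only the sum σ² matters, and it is estimable. In a simulated data set with this design, participant shares of 0, 10, 25, 50, 75, 90 and 99.9% of the variance all gave the same REML log-likelihood (−79.98944) and the same standard error of the contrast (0.05817), which is also the ANCOVA standard error.

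**Step 2: Kenward-Roger.** The information matrix for the two variances is k × J, where J is the 2×2 matrix of ones and k = (N − p)/(2σ⁴). It has rank 1 and determinant 0. The df of a single contrast with variance cσ² are

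f = 2(cσ²)² / (g′Wg), with g = c(1, 1)′ and W an inverse of kJ.

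Any generalised inverse satisfies (kJ)W(kJ) = kJ, which forces (1, 1)W(1, 1)′ = 1/k. So g′Wg = c²/k = 2c²σ⁴/(N − p), and

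f = 2c²σ⁴ × (N − p)/(2c²σ⁴) = N − p = 207 − 7 = 200.

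The small-sample correction to the variance is built from X′X/σ⁶ − (X′X/σ⁴) · σ²(X′X)⁻¹ · (X′X/σ⁴) = 0, so the standard error is not altered. Three inverses were tried numerically (Moore-Penrose, participant component set to zero, residual component set to zero). Each gave 200 df and 0.05817.

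**Step 3: the fallbacks.** For a single observation, AR(1) is σ² whatever the correlation, compound symmetry is the sum of its two parameters, and unstructured and Toeplitz are each one variance. All lead back to V = σ²I, so all give the same ratio and interval if they fit.

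**Step 4: how much a wrong df could matter.** For an observed ratio of 1, CV 38.5% and 69 per group, limits are exp(± t × 0.0633):

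| df | t | 90% CI |
|---|---|---|
| 100 | 1.6602 | 0.9002 to 1.1108 |
| 136 | 1.6561 | 0.9005 to 1.1105 |
| 200 | 1.6525 | 0.9007 to 1.1103 |
| infinite | 1.6449 | 0.9011 to 1.1097 |

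The widest movement is 0.0009 at the lower limit and 0.0011 at the upper.

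**Step 5: a literal fit.** A random-intercept fit in a Python package warned that its Hessian was not positive definite, split the variance 50/50 (0.0571 each, total 0.1142, equal to the ANCOVA residual variance), and reported a standard error of 0.05766 instead of 0.05817. At 200 df the half-widths on the log scale are 1.6525 × 0.05766 = 0.0953 and 1.6525 × 0.05817 = 0.0961, a difference of 0.0008.

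**The case for a change.** The strongest case for a change is that a primary analysis section should run as written, and this one does not. A literal matrix inverse fails; two programmers could report different df, or one could work through four structures to no purpose, and neither would breach the SAP. SAP 4.14 carries the problem further: it repeats the primary analysis without two sites, adds subgroup models patterned on 4.10.4, and leaves their specification to table footnotes. Correcting it would cost only wording.

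Most of this stands as description: the random effect is redundant, the fallback list cannot apply, and the labels conflict. What does not stand is the harm. Step 2 holds for any N and p, so the two-site exclusion and the subgroups also come back to ANCOVA with N − p degrees of freedom. Working through the fallbacks cannot favour a result, because each one that fits gives the same interval. If none runs cleanly, the obvious remedy is to drop the participant term, which gives that same ANCOVA. SAP 4.10.4.1 keeps the sponsor blinded to summary outputs until database lock, and protocol 11.2.1 requires model assumptions to be verified and documented and departures to be reported in the study report.

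One could also ask whether fitting one model per parameter to all study data means stacking the analytes, which would create repeated rows. The SAP lists the analytes as separate responses, gives no analyte term, and defines AZD7442 as the sum of the other two, so the text does not support that reading.

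**Conclusion.** The specification is untidy, but the primary result is fully determined. The treatment ratios, their standard errors, the 200 degrees of freedom and the 90% CIs are those of an ordinary ANCOVA on log values with the stated covariates. A df mistake as large as 100 or infinity in place of 200 would move a limit by about 0.001, and no realistic comparability conclusion turns on that. Power at the largest planning CV is 93.8% with either 136 or 200 df. An analyst meeting the convergence message will reach the ANCOVA by any sensible route, so rewriting the section would gain clarity and nothing else.

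This rests on one value per participant per parameter and analyte, on separate models by analyte, and on all 207 planned participants being evaluable; with fewer, df become N − 7 and the argument is unchanged. The numerical checks used simulated covariates and outcomes, but the algebra in steps 1 to 3 does not depend on them. The SAP names SAS 9.4, which was not run here. The Python warning therefore shows what one package does with a redundant variance and is no evidence of how SAS would behave.
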